### I-HoME intervention

The current I-HoME protocol involves video visits with a nurse practitioner for up to six visits to address symptom management and care needs. Nurse practitioners delivering the intervention go through a training session that familiarizes them with the I-HoME protocol. The protocol provides a framework for assessing/evaluating common patient symptoms and developing a treatment plan dependent upon the symptoms uncovered. After each visit, a summary of the treatment plan will be relayed to the patient's care team at the Center on Aging and/or the House Call program.

### **Data collection**

Patient variables will be collected from the electronic medical record and are detailed in **Table 1**. Validated surveys and questions will be administered to the caregiver via phone by a research assistant. Caregivers will be assessed on the measures listed in **Table 2** at various timepoints in the intervention. Participants

Table 1. Variables collected from the patient's electronic medical record							
Demographic data	Post-intervention measures						
Age	Number of office visits at Weill Cornell						
Gender	Number of phone calls at Weill Cornell						
Race/ethnicity	Hospitalization at Weill Cornell during intervention						
ADRD diagnosis code	Enrolled into hospice care during intervention (yes/no)						
Comorbidities							
Medications							
DNR/DNI status at							
time of enrollment							

will be compensated with a \$25 gift card each time they complete an initial, within study, and post-intervention survey phone call.

Baseline measures	Within study measures (After each visit)	Post-intervention measures (After final visit)		
Age	BPSD (NPI  )	BPSD (NPI2  )		
Gender	Pain (Doloplus-2  )	Depression (PHQ-88)		
Race/ethnicity	Burden (ZBI-short version  )	Anxiety (GAD-79)		
Religion/Spirituality	Depression (PHQ-88)	Acceptability measures		
Education	Anxiety (GAD-79)	Pain (Doloplus-2  )		
Relationship to patient	Software issues	Burden (ZBI-short version  )		
Hours providing care to patient	Hardware issues	Software issues		
Occupation		Hardware issues		
Income		Caregiving Preparedness 		

Caregiving Competence  SF-12 Health Survey 
SE 12 Hoalth Survoy2
3F-12 Health Survey
Family Satisfaction with Advanced Cancer Care 
26

Positive aspect of caregiving

Neuropsychiatric Inventory

Patient Health Questionnaire-8

SF-12 Health Survey

Doloplus-2

General Anxiety Disorder-7

Caregiving preparedness
Caregiving competence

Zarit Burden Interview–short version

Family Satisfaction with Advanced Cancer Care

### 3.2 Interviews, Focus Groups, Surveys, and/or Observations

#### A. Administration

For Aim 1 of the study, participants will be interviewed for up to 60 minutes to provide feedback on the I-HoME intervention. The same participants will be contacted within 2 months to provide additional feedback on the adapted version intervention; a follow-up questionnaire has been submitted to the IRB.

For Aim 2 of the study, questions will be administered to participants (family caregivers) at the first visit and within a week of completion of each televisit. Data from the subject's medical record will be obtained that are relevant to the study objectives (Table 2).

#### B. Study Instruments

For Aim 1, demographic measures will be collected from participants. A semi-structured interview guide will be used to conduct interviews, with open-ended questions.

For Aim 2, baseline demographic measures will be collected from the family caregiver and from the patient's medical record (see Table 1). Caregivers will be administered baseline, in-study, and post-intervention measures as outlined in Table 2.

#### 4. Study Design

# 4.1 Study Population – All Aims

Caregiver Participants: Family caregivers of ADRD patients who meet the following criteria: age ≥ 65 years old and < 105 years old with advanced ADRD (more details below)

Provider Participants: Healthcare providers from Weill Cornell Medicine or Hospice medical directors

#### 4.2 Inclusion Criteria

#### Aim 1

Healthcare provider criteria

- age 18 years or older
- a practicing medical provider (i.e., physician, nurse practitioner, physician assistant)
- experience working with caregivers of patients with ADRD
- English speaking.

#### ADRD LAR criteria

- age ≥ 18 years old and < 100 years

- English speaking
- Providing care to an ADRD patient who is age ≥ 65 years old and < 105 years

#### Aim 2

ADRD family caregiver criteria

- age ≥ 18 years old and < 100 years

- English speaking
- Providing care to an ADRD patient who is age ≥ 65 years old and < 105 years that is a stage 7a-f on the FAST scale
- Has access to an electronic device with cellular data or Internet connection

### 4.3 Exclusion Criteria - All Aims

Healthcare provider criteria

- Non-English speaking
- <18 years old

### ADRD LAR/family caregiver criteria

- Non-English speaking
- <18 years old or >100 years old
- Does not provide care to an ADRD patient who is age ≥ 65 years old and < 105 years that is a stage 7a-f on the FAST scale
- Does not have access to an electronic device with cellular data or Internet connection

# 4.4 Strategies for Recruitment and Retention

Participants will consist of healthcare providers and caregivers of patients with a history of advanced ADRD. Recruitment of participants will be conducted at Weill Cornell Medicine's Center on Aging (Aim 1 and Aim 2) and the hospice medical director website (Aim 1 only).

Patient referral will be obtained from providers of the practice. Providers will present an Agree to Contact Sheet (included with our IRB submission) when appropriate. Potential participants will be sent a recruitment letter by a member of the research team to inquire about participating. We will follow up with family caregivers of the patients to whom we've sent a recruitment letter, via phone call or e-mail, one week following the mailing.

We will not target sample size by gender, race or ethnicity but hope to have a diverse pool of participants. We hope to recruit a total of 90 participants and estimate that we will screen 300 potential participants. A partial HIPAA waiver for recruitment purposes is requested in the IRB application. After a potential caregiver participant has been identified (for Aim 2) via our recruitment methods, study staff will review

charts and a study team physician will approve that a potential participant is medically eligible before consent and screening occurs.

Participants in Aim 1 will be compensated with a \$75 gift card for their participation. Participants in Aim 2 will be compensated with a \$25 gift card after completion of surveys during the duration of the study.

# 5. Registration Procedures

# 5.1 Subject Registration (WCM only)

Subjects will be registered within the WRG-CT as per the standard operating procedure for Subject Registration.

# 6. Study Procedures

#### **6.1 Schedule of Assessments**

Table 3. Schedule of trial events

AIM 1	Pre- Study	Time point 1	Time point 2
Screening (providers and LARs)	X		
Informed Consent		Х	
Demographic Questions and interview		Х	
Follow up interview for feedback on adapted version of I-HoME			Х

Table 4. Schedule of trial events

AIM 2	Pre- Study	Day 1 (Study Visit)	Post visit #1	Post visit #2	Post visit #3	Post visit #4	Post visit #5	Post visit #6
Screening (Patient)	Х							
Screening (Family caregiver)	Х							
Informed Consent		Х						
Demographic Questions		Х						
Family caregiver survey data collection		Х	Х	Х	Х	Х	Х	Х

# 7. Data Reporting / Regulatory Considerations

#### 7.1 Data Collection

The data collection plan for this study is to utilize REDCap to capture data (Demographic, medical and survey data) for all enrolled subjects.

### **7.1.1 REDCap**

REDCap (Research Electronic Data Capture) is a free data management software system that is fully supported by the Weill-Cornell Medical Center CTSC. It is a tool for the creation of customized, secure data management systems that include Web-based data-entry forms, reporting tools, and a full array of security features including user and group-based privileges, authentication using institution LDAP system, with a full audit trail of data manipulation and export procedures. REDCap is maintained on CTSC-owned servers that are backed up nightly and support encrypted (SSL-based) connections. Nationally, the software is developed, enhanced, and supported through a multi-institutional consortium led by the Vanderbilt University CTSA.

# 7.2 Regulatory Considerations

# 7.2.1 Institutional Review Board/Ethics Committee Approval

As required by local regulations, the Investigator will ensure all legal aspects are covered, and approval of the appropriate regulatory bodies obtained before study initiation.

Before initiation of the study at each study center, the protocol, the ICF, other written material given to the patients, and any other relevant study documentation will be submitted to the appropriate Ethics Committee. Written approval of the study and all relevant study information must be obtained before the study center can be initiated or the IP is released to the Investigator. Any necessary extensions or renewals of IEC/IRB approval must be obtained for changes to the study, such as amendments to the protocol, the ICF, or other study documentation. The written approval of the IEC/IRB together with the approved ICF must be filed in the study files.

The Investigator will report promptly to the IEC/IRB any new information that may adversely affect the safety of the subjects or the conduct of the study. The Investigator will submit written summaries of the study status to the IEC/IRB as required. On completion of the study, the IEC/IRB will be notified that the study has ended.

All agreed protocol amendments will be clearly recorded on a protocol amendment form and will be signed and dated by the original protocol approving signatories. All protocol amendments will be submitted to the relevant institutional IEC/IRB for approval before implementation, as required by local regulations. The only exception will be when the amendment is necessary to eliminate an immediate hazard to the trial participants. In this case, the necessary action will be taken first, with the relevant protocol amendment following shortly thereafter.

Once protocol amendments or consent form modifications are implemented at the lead site, Weill Cornell Medicine, updated documents will be provided to participating sites. Weill Cornell Medicine must approve all consent form changes prior to local IRB submission.

Relevant study documentation will be submitted to the regulatory authorities of the participating countries, according to local/national requirements, for review and approval before the beginning of the study. On completion of the study, the regulatory authorities will be notified that the study has ended.

# 7.2.2 Ethical Conduct of the Study

The Investigators and all parties involved should conduct this study in adherence to the ethical principles based on the Declaration of Helsinki, GCP, ICH guidelines and the applicable national and local laws and regulatory requirements.

This study will be conducted under a protocol reviewed and approved by the applicable ethics committees and investigations will be undertaken by scientifically and medically qualified persons, where the benefits of the study are in proportion to the risks.

#### 7.2.3 Informed Consent

The investigator or qualified designee must obtain documented consent according to ICH-GCP and local regulations, as applicable, from each potential subject or each subject's legally authorized representative prior to participating in the research study. Subjects who agree to participate will complete an informed consent process and will be provided a copy of the finalized document.

Informed Consent for participants will occur just prior to their screener by in person or remote, oral consent methods. A member of the study team will review the ICF document, in-full, with each participant in person or by phone or videoconference, emphasizing the key information, allowing for questions, and reminding the potential subject that participation is entirely voluntary. In person and oral confirmation of consent will be documented by the study team member.

The initial ICF, any subsequent revised written ICF and any written information provided to the subject must approved by IRB prior to use. The ICF will adhere to IRB/IEC requirements, applicable laws and regulations.

### 7.2.4 Compliance with Trial Registration and Results Posting Requirements

Under the terms of the Food and Drug Administration Modernization Act (FDAMA) and the Food and Drug Administration Amendments Act (FDAAA), the Sponsor-Investigator of the trial is solely responsible for determining whether the trial and its results are subject to the requirements for submission to http://www.clinicaltrials.gov. Information posted will allow subjects to identify potentially appropriate trials for their disease conditions and pursue participation by calling a central contact number for further information on appropriate trial locations and trial site contact information.

#### 7.2.5 Record Retention

Essential documents are those documents that individually and collectively permit evaluation of the study and quality of the data produced. After completion of the study, all documents and data relating to the study will be kept in an orderly manner by the Investigator in a secure study file. Essential documents should be retained for 2 years after the final marketing approval in an ICH region or for at least 2 years since the discontinuation of clinical development of the IP. In addition, all subject medical records and other source documentation will be kept for the maximum time permitted by the hospital, institution, or medical practice.

#### 8. Statistical Considerations

Aim 1

Audio recordings from interviews will be transcribed verbatim. Content analysis, a method for classifying verbal and behavioral data into categories of similar meaning, will be used to analyze data. A deductive approach will be implemented. During open coding, short sections of text representing discrete concepts will be identified from transcripts and tagged with a code. This will be followed by focused coding, which involves comparing codes within and across interviews. Lastly, axial coding, where codes are compared between transcripts to develop a set of categories and/or themes, will be the third step of the coding process. A code book will be developed to systematize data analysis and ensure findings are reproducible. Interrater reliability and trustworthiness will be evaluated as part of the qualitative analytic process. Two individuals with varied

backgrounds will independently review and code the transcripts. Discrepancies will be resolved through discussion until consensus is reached.

#### Aim 2

Feasibility will be assessed by examining accrual rates, attrition rates, adherence to the study protocol, hardware issues, software issues, and use of the intervention (e.g., frequency and duration of visits). Within study measures will be collected after every video visit to examine feasibility and acceptability of the intervention. Furthermore, an acceptability questionnaire will be administered at the end of the study to caregivers to obtain feedback on the intervention as a whole.

Quantitative care outcomes being collected fall into three main categories: patient outcomes (e.g., symptom-related measures), caregiver outcomes (e.g., burden, depression, anxiety, satisfaction, preparedness, competence, caregiver health), and healthcare utilization outcomes (e.g., number of visits, hospitalizations). Given the scope of this proposal, the number of caregiver participants (n=30) proposed for this study is aimed at establishing feasibility and acceptability and not efficacy. However, we will conduct preliminary efficacy analysis on outcomes at baseline and post intervention. Looking at pain (Doloplus-2 scale) as one of the secondary outcomes, with the assumption of a 40% improvement in scores based on a mean of 8.3 and SD of 6.5, there will be 80% power to detect an effect size of d=0.5, which is considered a moderate effect.

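### Section 8 disclaims efficacy for Aim 2, then plans a powered preliminary efficacy analysis of before-after change with no comparator, so the result cannot be attributed to I-HoME

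*Combined protocol and SAP*

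**What the plan says.** All the statistical text for Aim 2 is in Section 8 of the combined protocol and SAP. It states that "the number of caregiver participants (n=30) proposed for this study is aimed at establishing feasibility and acceptability and not efficacy". The next sentence turns on a However: "we will conduct preliminary efficacy analysis on outcomes at baseline and post intervention". Pain on the Doloplus-2, named as one of the secondary outcomes, is then used for a power statement: "with the assumption of a 40% improvement in scores", "based on a mean of 8.3 and SD of 6.5", leading to "there will be 80% power to detect an effect size of d=0.5, which is considered a moderate effect". Section 8 gives no test, significance level, sidedness, missing-data rule or caution about attribution.

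Elsewhere the protocol describes one group of 30 caregivers, all offered the intervention. No control, randomisation or historical benchmark appears. The Protocol Summary (Section 1) limits the Aim 2 objective to feasibility and acceptability and lists secondary and exploratory objectives as not applicable. Its primary endpoints are the percentages of caregivers who enrol and who complete the telehealth visits.

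**The concern.** The label and the design do not match. An efficacy analysis asks whether the intervention changed the outcome. A before-after difference in one group shows only that the outcome changed. The protocol itself points to several other sources of change:

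- Patients are at FAST stage 7a-f (Section 4.2), and the plan gives no estimate of their natural course.
- The intervention is added to existing care (Section 2), and visit summaries go to the usual care team (Section 3.1, I-HoME intervention).
- Hospice enrolment and hospitalisation during the intervention are recorded (Section 3.1, Table 1), but no handling of either is planned.
- The scales are administered to the caregiver, who also receives the intervention and so is not blinded to it.

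The bias could go either way. Natural worsening could hide a benefit, and better care from another source could look like one. The power statement adds to the difficulty, because it presupposes a test of change and gives the comparison a formal standing that the preceding sentence had just declined.

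**Working it through.** **Inputs from Section 8.** n=30; mean 8.3; SD 6.5; improvement 40%; power 80%; d=0.5.

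**Assumptions.** Two-sided 5% level, which is not stated. SD of change equal to 6.5 for the first two steps, because Section 8 does not say whether 6.5 describes scores or within-person change.

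**1. Reproduce the stated power.** The assumed improvement is 0.40 × 8.3 = 3.32 points, and 3.32 / 6.5 = 0.511, which the plan gives as 0.5. For a before-after test under the normal approximation, power = Φ(d√n − 1.96):

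- d=0.5: Φ(2.739 − 1.960) = Φ(0.779) = 78.2%
- d=0.511: Φ(2.798 − 1.960) = Φ(0.838) = 79.9%

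So the 80% is reproduced, approximately, as a one-group test on 30 complete pairs. It does not fit a two-group comparison: 15 per arm gives Φ(0.5 × √7.5 − 1.96) = Φ(−0.591), about 28%. A one-sided 5% test gives 85% to 88%, which does not match either. The power figure therefore confirms that a within-group before-after test is meant.

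**2. Paired t-test and attrition.** Using the noncentral t with n−1 degrees of freedom:

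| Complete pairs | d=0.5 | d=0.511 |
|---|---|---|
| 30 | 75.4% | 77.2% |
| 24 | 65.0% | 66.9% |

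By t-test, 80% power needs 34 pairs at d=0.5 or 33 at d=0.511. The figure of 24 pairs (20% loss) is an assumption. Section 8 lists attrition as a feasibility measure but makes no allowance for it in the power statement.

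**3. How the test responds to change from other causes.** If 6.5 is the cross-sectional SD, the SD of change is 6.5 × √(2(1−ρ)): 5.03 at ρ=0.7, 6.5 at ρ=0.5 and 7.69 at ρ=0.3. The documents give no correlation and no drift, so the following is illustrative only. Take a drift of 1.3 points (0.2 × 6.5), no intervention effect, 30 pairs and a paired t-test:

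| SD of change | Standardised drift | Probability of p<0.05 |
|---|---|---|
| 5.03 | 0.258 | 28% |
| 6.5 | 0.200 | 19% |
| 7.69 | 0.169 | 15% |

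The argument does not depend on the size chosen. The test has the same chance of significance for a given mean change, whatever caused it.

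**4. Expected precision.** The 95% confidence interval half-width is t(0.975, n−1) × SD / √n.

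| SD of change | 30 pairs (t=2.045) | 20 pairs (t=2.093) |
|---|---|---|
| 5.03 | 1.9 | 2.4 |
| 6.5 | 2.4 | 3.0 |
| 7.69 | 2.9 | 3.6 |

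**The case against.** The strongest reply is that the plan already subordinates this analysis. It says the sample is "aimed at establishing feasibility and acceptability and not efficacy", calls the analysis preliminary, powers only a secondary outcome, and states a hypothesis about feasibility and acceptability alone. The power sentence does not set n, and no primary conclusion rests on it. Table 1 also collects hospitalisations, office visits, phone calls and hospice entry, so some competing explanations can at least be described. All of this stands, and it confines the point to interpretation and labelling. It does not remove the point: the word preliminary speaks to precision, not to the absence of a comparator.

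A second reply is that a confidence interval is no cure. A 95% interval for mean change excludes zero exactly when the paired t-test gives p<0.05, and drift shifts both alike. That is correct. The essential part of the fix is the statement of non-attribution, not the change from test to interval.

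Three stronger readings are not supported:

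- A reader might infer that a significant p-value will be reported as efficacy and a null result as lack of it. Section 8 sets no decision or reporting rule.
- A reader might infer that some patients will enter hospice. Table 1 shows only that entry would be recorded.
- A reader might say that the 80% is simply wrong. It is close under a normal approximation with no loss, and optimistic under a t-test or with attrition.

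**Conclusion.** The concern holds as a mismatch between label and design. Section 8 plans an efficacy analysis, with a power statement, for a before-after comparison that cannot attribute change to I-HoME. That the group is single is inferred from the absence of any comparator, since the documents do not use the term; the power figure supports the inference. The 15% to 28% for a 1.3-point drift rests on assumed values for the drift and the SD of change, and it shows how the test behaves rather than predicting what will happen. The claim that "there will be 80% power to detect an effect size of d=0.5" is approximate at best, for the reasons in the working. The feasibility endpoints and the choice of n=30 are not affected. The plan should be changed because the correction alters what the pilot may conclude at almost no cost.

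**What to change.** Change two sentences in Section 8.

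- In place of the preliminary efficacy analysis, write: descriptive estimation of within-person change from baseline (mean change with 95% CI), which will not be attributed to the intervention.
- In place of the power sentence, give expected precision as a range: for an assumed SD of change of 5.0 to 7.7, the 95% CI half-width for mean Doloplus-2 change is 1.9 to 2.9 points with 30 complete pairs and 2.4 to 3.6 with 20.

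Add that the observed SD of change and baseline-post correlation will be used to plan a controlled trial.

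This needs no extra participants, visits or instruments. The cost is giving up a preliminary efficacy claim and a power figure.
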